M09. In the investigator's opinion, the participant is able to understand and comply with protocol requirements, instructions, and study restrictions (Section [5.3, Lifestyle Considerations](#)) and is likely to complete the study as planned in this ISA (including the

procedures outlined in the Master Protocol PLATFORMPAHPB2001).

A05. Participants must have HBsAg >100 IU/mL at screening.

A06. Participants must have:

- Fibroscan liver stiffness measurement ≤ 9.0 kPa within 6 months prior to screening or at the time of screening, OR
- If a fibroscan result is not available: a liver biopsy result classified as Metavir F0-F2 within 2 years prior to screening or at the time of screening.

Note: Other radiologic liver staging modalities (eg, acoustic radiation force impulse) might be used if standard practice at the site or if otherwise validated and agreed with the sponsor. Results should be equivalent to Metavir F0-F2 with absence of signs of portal hypertension.

Note: Conventional imaging procedures alone (eg, conventional liver ultrasound, computed tomography [CT] or magnetic resonance imaging [MRI]) and serum marker panels are not allowed to rule out severe fibrosis or cirrhosis.

A07/ M10. Male participants must agree to wear a condom when engaging in any activity that allows for passage of ejaculate to another person during the study intervention phase and until 90 days after last dose of study intervention.

A08. Female participants must agree not to donate eggs (ova, oocytes) for the purposes of assisted reproduction during the study intervention phase and until 90 days after last dose of study intervention.

A09. Male participants must agree not to donate sperm for the purpose of reproduction during the study intervention phase and until 90 days after the last dose of study intervention.

Note: Retesting to assess eligibility will be allowed once, using an unscheduled visit during the screening period.

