5.2.2.1.4. Missing Data Handling Rule

Participants who withdraw from the study prior to Week 72 will be considered as non-responders.

If a participant remains in the study after experiencing a major protocol deviation (defined for the purpose of efficacy analyses and is an intercurrent event) and has missing Week 72 value, then the imputation to non-response will be applied. If the value for the endpoint at Week 72 is available, then such data will be used to determine their response status.

For the participants still in the study at Week 72 or for participants that have neither discontinued treatment early nor experienced any major protocol violations (defined for the purpose of efficacy analyses and is an intercurrent event), and HBsAg values missing at Week 72, then the primary

method to handle missing data will be the Multiple Imputation (MI) approach ([Ratitch B. et al., 2013](#)) under the assumption of MAR will be applied to a model for continuous HBsAg log values over time.

The MI model will use all available data and be applied to the continuous log-transformed HBsAg values (not the binary endpoint). Of note, also the pre-ICE data for those subjects who experienced an ICE will be included in the MI model; but for these subjects the response status will be applied according to the ICE strategies before running the MI model.

The model will include treatment, the 2 randomization factors (race [Asian versus non-Asian] and type of NA [TDF/TAF versus ETV]) and the available non-missing log-transformed HBsAg (values < LLOQ, TND or TD will be first substituted following rules described in [Table 3](#)) for each scheduled time point (Week) and the following demographic and baseline characteristics ([King G. et al., & Honaker J. et al.](#)): age, gender, and baseline log-transformed value for HBsAg level.

A total of 200 datasets will be generated where both intermittent and monotone missing HBsAg values will be imputed for each subject relying on non-missing data from all other subjects within the same treatment group. Once the 200 completed datasets are generated by filling in the missing data with samples from the imputation model, the primary endpoint response status (binary variable) will be derived using both imputed and observed HBsAg values at Week 72.

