5.3.2.2.1. HBsAg and HBV DNA

The change from baseline value to the nadirs (i.e. maximum decrease for each participant) in HBsAg and HBV DNA will be summarized descriptively by intervention arm. Box plots of the changes to nadirs in HBsAg and HBV DNA will display the distribution by intervention arm.

Change from baseline based on \log_{10} transform for quantitative HBsAg and HBV DNA will be analyzed using mixed effects model for repeated measures [MMRM]) including intervention arm, analysis time point (week), their interaction, and 3 randomization stratification factors (screening HBsAg level [$<1,000$ IU/mL or $\geq 1,000$ IU/mL], race [Asian versus non-Asian] and type of NA [TDF/TAF versus ETV]) and baseline blood marker categorical variable as fixed effects. In addition, the above model will be augmented with an intervention arm-by-analysis week interaction term (i.e. treatment-by-time interaction term) to evaluate the change of treatment effect over time and the intervention arm-by-baseline interaction term. The covariance structure will include a random intercept at the level of the participant to capture between-participant variability, while within-participant variability will be captured with an unstructured (type=UN) covariance matrix. In case of convergence problems, simpler variance-covariance structures such as Toeplitz or AR (1) will be considered. The selection of any of these structures will be determined after exploration of the observed correlation structure. The LS mean of change from baseline, standard error (SE), 90% confidence interval (CI) and p-values will be provided.

Descriptive statistics on actual values (original unit and \log_{10} transformed values) and changes from baseline (\log_{10} transformed values) at end of treatment in HBsAg and HBV DNA will be summarized by study intervention arm by outcome response (i.e. by functional cure status at Week 72, and by partial cure status at Week 72).

Spaghetti plots for both absolute values and changes from baseline of HBsAg and HBV DNA will be presented over time per blood marker by intervention arm and by selected subgroups (e.g. HBV Genotype) and by outcome response (i.e. by functional cure status at Week 72, and by partial cure status at Week 72).

Cross-tabulations overtime and overall of quantitative versus qualitative HBsAg values will also be presented.

Shift tables in HBV DNA categories from baseline will also be summarized by study intervention arm.

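### The repeated-measures model for HBsAg and HBV DNA carries a redundant random intercept, falls back on equal-variance structures chosen after looking at the data, and categorises baseline HBsAg

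*SAP*

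**What the plan says.** SAP 5.3.2.2.1 fits one mixed model for repeated measures to change from baseline in log10 HBsAg and HBV DNA.

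- **Covariance.** The first component is given as: "The covariance structure will include a random intercept at the level of the participant to capture between-participant variability". For the residual component, the same sentence adds that "within-participant variability will be captured with an unstructured (type=UN) covariance matrix".
- **Fallback.** "In case of convergence problems, simpler variance-covariance structures such as Toeplitz or AR (1) will be considered". Then: "The selection of any of these structures will be determined after exploration of the observed correlation structure". No order is given.
- **Baseline.** The marker enters as a "baseline blood marker categorical variable as fixed effects", with no cut-points named in that section. The model also holds the "3 randomization stratification factors (screening HBsAg level" split at 1,000 IU/mL, race and type of NA).
- **Weeks.** The section does not say which analysis weeks are modelled. SAP 2.1.3, Table 2, lists 13 post-baseline double-blind windows and 15 follow-up windows.

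Least-squares means, standard errors, 90% CIs and p-values will be reported. SAP 5.3.2 makes no multiplicity adjustment for secondary endpoints.

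**The concern.** An unstructured matrix already contains any variance shared across a participant's visits, so a random intercept on top cannot be estimated separately. That is a specification error, though a harmless one in itself.

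The larger issue is what happens if the unstructured fit fails. Standard Toeplitz and AR(1) use a single variance for all weeks. HBV DNA is unlikely to behave that way. Entry requires less than 60 IU/mL (Protocol 5.1), and values below the 20 IU/mL LLOQ are set to 15 or 5 IU/mL (SAP 5.1.2, Table 3), so on-treatment values should be nearly constant. After NA is stopped, the Protocol expects rebound in most patients (2.1) and sets re-treatment thresholds up to 100,000 IU/mL (6.7). The spread of HBsAg change may also grow during treatment. A pooled variance then understates the error at the late weeks, which are the ones of interest, and overstates it early.

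The categorised baseline is a separate matter of precision. It applies to HBsAg, which is measured on a wide continuous scale.

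**Working it through.** **The plan's own figure.** The documents give no operating characteristic for this model. The only stated figure is power above 91% for the primary endpoint (5% versus 25%, 40 versus 80, one-sided 0.05). Exact enumeration of the unstratified Mantel-Haenszel test gives 91.7%, so it reproduces. It does not depend on this model.

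**1. Redundancy.** Write the covariance as V = σ_b²J + R, with J a matrix of ones and R unstructured. R has T(T+1)/2 parameters.

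| Windows T | Unstructured alone | With random intercept | Rank |
|---|---|---|---|
| 13 (double-blind) | 13×14/2 = 91 | 92 | 91 |
| 26 (scheduled visits) | 26×27/2 = 351 | 352 | 351 |
| 28 (all Table 2 windows) | 28×29/2 = 406 | 407 | 406 |

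Exactly one parameter is redundant each time. Toeplitz plus random intercept has the same fault (14 parameters, rank 13 at T = 13). AR(1) plus random intercept does not (3 of 3). In a four-visit example, σ_b² = 0, 0.1, 0.2 and 0.3 gave the same log-likelihood (-18.188243) and the same standard error of the last-visit arm contrast (0.16287).

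**2. Equal-variance fallback.** With complete data and an arm-by-week term, the arm difference at week t is the difference in cell means. Its true standard error is SD_t × √(1/80 + 1/40). An equal-variance model reports σ̂ × √(1/80 + 1/40). The ratio is therefore σ̂/SD_t, and the actual one-sided error at nominal 5% is 1 − Φ(1.645 × ratio).

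The documents give no SDs, so those below are assumptions. The true correlation between adjacent visits is 0.8 to 0.9, and the random intercept is dropped.

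| Assumed SD of change | Ratio at last visit, AR(1) | One-sided error |
|---|---|---|
| HBsAg, 13 windows, 0.3 rising to 0.7 | 0.74–0.75 | about 11% |
| HBsAg, 13 windows, 0.1 rising to 0.8 | 0.65–0.66 | about 14% |
| HBV DNA, 28 windows, 0.2 on and 1.0 off treatment | 0.74 | about 11% |
| HBV DNA, 28 windows, 0.2 on and 1.5 off treatment | 0.73–0.74 | about 11% |

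Hand check for the third row: the root mean square SD is √[(13×0.2² + 15×1.0²)/28] = √(15.52/28) = 0.74, and 1 − Φ(1.645×0.74) = 0.11. In the two HBV DNA rows the on-treatment standard errors are about 3.7 and 5.5 times too large.

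**3. Categorised baseline HBsAg.** Let ρ be the correlation of baseline with change, and R²cat the share of baseline variance that the categories keep. The standard error is inflated by √[(1 − ρ²R²cat)/(1 − ρ²)].

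Assumed: baseline log10 HBsAg normal with mean 3.0 to 3.6 and SD 0.5 to 0.7, cut at 2 because "Participants must have HBsAg >100 IU/mL at screening". The categories are the three levels in SAP 2.4.1 (below 1,000; 1,000 to below 10,000; 10,000 and above). R²cat is then 0.72 to 0.81.

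- ρ = 0.3: from √[(1 − 0.09×0.81)/0.91] to √[(1 − 0.09×0.72)/0.91], an inflation of 0.9 to 1.4%.
- ρ = 0.5: from √[(1 − 0.25×0.81)/0.75] to √[(1 − 0.25×0.72)/0.75], about 3.0 to 4.6%.
- ρ = 0.7: about 9 to 13%.

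The SAP's own imputation model for the primary endpoint (5.2.2.1.4) uses the "baseline log-transformed value for HBsAg level", so the continuous value is at hand.

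**The case against.** Several stronger readings are tempting, and the documents do not support them.

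- **That the redundancy forces the analysis into a fallback.** It does not. The SAP moves to a simpler structure only if convergence fails, and a fit with the intercept variance at zero is simply the unstructured model. Any convergence trouble comes more from the number of visits, and dropping the intercept would not remove that.
- **That the redundancy costs precision.** It does not; likelihood and standard error are unchanged. The precision loss comes only from categorising baseline.
- **That 406 parameters is the plan.** It is an upper bound. The weeks are not stated, and Table 2 includes Follow-up Weeks 30 and 42, which are not in the current visit schedule (Protocol 1.3.2).
- **That baseline should be continuous for both markers.** For HBV DNA, baseline is mostly imputed constants below 20 IU/mL, and SAP 2.4.1 already groups it by detection status. A category is a reasonable coding there.

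It can also be said that inspecting the observed correlations is meant to prevent a poor fit, and that the two structures are only examples. This stands in part: a heterogeneous structure is not excluded. But both named candidates are equal-variance forms, looking at correlations need not reveal unequal variances, and no order is fixed. The SAP (1.5) also has the sponsor's central team unblinded from the Week 48 interim analysis, and does not say whether the structure is chosen before that.

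Finally, these are secondary endpoints. Descriptive summaries of the same changes are planned regardless (SAP 5.3.2.2). That limits the consequence and is accepted.

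**Conclusion.** The point holds in a limited form. The covariance is over-parameterised by exactly one parameter, with no effect on the arm contrast. Convergence problems are plausible but not certain with 120 participants and 91 to 406 unstructured parameters. If AR(1) with model-based standard errors is then used, late-visit standard errors could be about 0.65 to 0.75 of the true value and the one-sided error about 11 to 14%. Those figures rest on assumed SDs, adjacent-visit correlations of 0.8 to 0.9 and complete data; with stable variance over time the distortion would vanish.

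Categorising baseline HBsAg costs about 1 to 5% in standard error at assumed correlations of 0.3 to 0.5, given the three-level coding. For HBV DNA the loss is probably negligible.

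A reader might infer that the main result of the trial is at risk. It is not: the primary endpoint uses the stratified Mantel-Haenszel difference, and neither that test nor its stated power depends on this model.

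**What to change.** Revise SAP 5.3.2.2.1 as follows:

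1. Drop the random intercept and use the unstructured matrix alone. Drop it under Toeplitz too.
2. Name the weeks modelled, and fit double-blind and follow-up visits separately.
3. Use continuous log10 baseline HBsAg in the HBsAg model. Keep a categorical baseline for HBV DNA and state its levels.
4. Replace the open choice with an ordered list of heterogeneous-variance fallbacks, for example heterogeneous Toeplitz, then ARH(1). Use small-sample-corrected sandwich standard errors for any structure other than unstructured.
5. List the arm-by-week interaction once; it now appears twice, which is editorial only.

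The cost is SAP wording and slightly more programming. Uncorrected sandwich standard errors can be biased with only 40 controls, so the correction is part of the change. No data collection, sample size or primary analysis is affected.

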5.3.2.3. Time to Event Endpoints

The Kaplan-Meier method will be used to estimate and plot the cumulative incidence by each intervention arm. The log-rank test will be performed to compare between the intervention arms. The median time with 90% CI will be estimated using Kaplan-Meier method. To explore the impact of selected baseline factors in addition of study intervention, the survival probabilities will be estimated based on a stratified Cox regression model including study intervention arm, and each baseline factor at a time with the intervention arm-by-baseline factor interaction term. The strata in the stratified Cox model are the 3 randomization stratification factors to allow for a separate baseline hazard for each level of those factors. The interaction between study intervention arm and baseline/disease characteristic will be explored graphically.

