In a recent systematic review that included 25 studies mainly from Asia, identification of predictors of virologic relapse and HBsAg loss after stopping NA led to conflicting results, partly due to the heterogeneity of the studies and low rate of HBsAg loss (2%).²⁹ Lower baseline HBsAg level was the only statistical baseline factor for off-therapy HBsAg seroclearance in a large cohort of 1075 HBeAg-negative patients in Taiwan.¹⁸ Studies conducted in Asia have reported a lower estimated annual incidence of 1.78% of HBsAg loss highlighting potential differences among Asians and Caucasians.¹⁸ A recent European retrospective, observational cohort study that included 198 NA-treated CHB patients who stopped NA treatment after HBeAg seroconversion showed 7-fold higher annual HBsAg seroclearance rates in Caucasian patients compared to non-Caucasians.³⁴

After stopping NA treatment, it is expected that most of the patients will have rebound of HBV DNA. This was reported in the Hadziyannis study where all patients had an initial rebound of HBV DNA and 76% showed an alanine aminotransferase (ALT) flare suggesting that virologic relapse might be an important trigger for immune response that could lead to subsequent HBsAg loss. This was also reported in a recent prospective study showing that level of HBV DNA after stopping NA was the most important factor for subsequent HBsAg decline.¹³ Therefore factors that may influence virologic relapse should be taken into consideration. Some recent studies have reported that patients treated with TDF experience virologic relapse significantly earlier than those receiving ETV. In a randomized study of 220 HBeAg-negative Asian patients who stopped treatment, 71% (47 of 66) treated with TDF had virologic relapse by Week 12, whereas 4.5% of patients (7 of 154) treated with ETV had virologic relapse in the same period ($p < 0.0001$), while the overall virologic relapse rate was similar.¹² Similarly, in a retrospective study that included 234 HBeAg-negative Asian patients who stopped treatment, median time to virologic relapse was 18 weeks (TDF) versus 33 weeks (ETV).²⁰

Given the reported influence of race (Asian versus non-Asian), type of NAs (TDF/tenofovir alafenamide [TAF] versus ETV) and baseline HBsAg level on virologic relapse and subsequently HBsAg seroclearance, those 3 elements will be included as stratification factors in the current study.

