6.3. Measures to Minimize Bias: Randomization and Blinding

Intervention Allocation

Procedures for Randomization and Stratification

Central randomization will be implemented in this study. Participants will be randomly assigned in a 2:1 ratio to 1 of 2 intervention arms (JNJ-3989+JNJ-6379+NA:placebo+placebo+NA). Randomization will be based on a computer-generated randomization schedule prepared before the study by or under the supervision of the sponsor. The randomization will be balanced by using randomly permuted blocks and will be stratified by screening HBsAg level (<1,000 IU/mL or \geq 1,000 IU/mL), race (Asian versus non-Asian) and type of NA (TDF/TAF versus ETV).

For more information on the interactive web response system (IWRS), refer to Section 6.3 of the Master Protocol PLATFORMPAHPB2001.

Blinding

The investigators and participants will remain blinded to intervention allocation until all participants have reached Week 72 (or discontinued earlier), while the sponsor's central study team will be unblinded at the time of the Week 48 IA.

Under normal circumstances, the blind should not be broken until all participants have completed Week 72 or discontinued earlier. The investigator may in an emergency determine the identity of the study intervention by contacting the IWRS. While the responsibility to break the study intervention code in emergency situations resides solely with the investigator, it is recommended that the investigator contacts the sponsor or its designee to discuss the particular situation, before breaking the blind, only if this does not delay action with respect to treatment in an emergency situation. Telephone contact with the sponsor or its designee will be available 24 hours per day, 7 days per week. In the event the blind is broken, the sponsor must be informed as soon as possible. The date, time, and reason for the unblinding must be documented by the IWRS, in the appropriate section of the CRF, and in the source document. The documentation received from the IWRS indicating the code break must be retained with the participant's source documents in a secure manner.

Sponsor personnel involved in the pharmacokinetic and pharmacodynamic modeling will have access to the pharmacokinetic and pharmacodynamic data before formal unblinding. Sponsor personnel involved in trial conduct, data management, and statistics will not have access to these data.

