The proportion of participants who reach HBV DNA <LLOQ and/or ALT normalization after restart of NA treatment during follow-up will also be tabulated by intervention arm and the comparison between the intervention arms will be done using the Mantel-Haenszel test for difference in proportions as described above.

The blood markers (such as HBsAg, HBV DNA, and ALT) during study intervention and follow-up will also be summarized by intervention arm over time and plotted. The proportion of participants with virologic breakthrough (on treatment) and the proportion of participants with (sustained) reduction, suppression, and/or seroclearance during follow-up considering single and multiple markers (such as HBsAg, HBV DNA, and ALT) will be summarized by intervention arm. The proportion of participants with HBsAg seroconversion will be tabulated by intervention arm. Descriptive statistics on values and changes from baseline over time in HBsAg and HBV DNA will be summarized by intervention arm. Additional summaries will be provided by the randomization stratification factors (screening HBsAg level [$<1,000$ IU/mL or \geq 1,000 IU/mL], race [Asian versus non-Asian] and type of NA [TDF/TAF versus ETV]).

The time to achieve first HBsAg seroclearance will be summarized based on Kaplan-Meier estimates in tables and graphs and compared between study interventions using the log rank test. The proportion of participants with HBsAg levels and/or changes from baseline below/above different cut-offs, and the proportion of participants with HBV DNA levels and/or changes from baseline below/above different cut-offs will be analyzed as appropriate by intervention arm and over time. The proportion of participants with ALT decrease and normalization will be tabulated by intervention arm.

Graphic data displays will also be used to summarize the efficacy data by intervention arm and over time.

In addition, the potential association between treatment outcome and baseline factors (including but not limited to screening HBsAg level [$<1,000$ IU/mL or \geq 1,000 IU/mL], race [Asian versus

non-Asian] and type of NA [TDF/TAF versus ETV], and other HBV and host characteristics) will be explored by multivariate analyses and exploration of interaction terms.² Exploratory subgroup summaries will be displayed graphically in forest plots.

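### The between-arm log-rank test names no strata although randomisation was stratified on three factors the protocol treats as prognostic: a minor, avoidable loss of power for the full-population time-to-event endpoints

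*SAP*

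**What the plan says.** SAP 5.3.2.3 gives one sentence on comparing arms: "The log-rank test will be performed to compare between the intervention arms". Protocol 9.4.1.2 says of time to first HBsAg seroclearance that it will be "compared between study interventions using the log rank test". Neither names strata, and nothing elsewhere adds them. SAP 5.4.2.3 carries the same method over to the exploratory time-to-event endpoints.

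On randomisation, Protocol 6.3 says: "The randomization will be balanced by using randomly permuted blocks and will be stratified by screening HBsAg level", and goes on to race and type of NA. Three two-level factors make 2 × 2 × 2 = 8 cells. Protocol 2.1 gives the reason, the reported influence of these factors "on virologic relapse and subsequently HBsAg seroclearance, those 3 elements will be included as stratification factors in the current study".

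The other main comparisons use the factors:
- the Mantel-Haenszel test for the primary endpoint (SAP 5.2.2.1.1) and for the selected seroclearance endpoints (SAP 5.3.2.1);
- the repeated-measures model for HBsAg and HBV DNA (SAP 5.3.2.2.1);
- the fibrosis ANCOVA (SAP 5.4.2.2.1).

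The Cox model in SAP 5.3.2.3 uses them too: "The strata in the stratified Cox model are the 3 randomization stratification factors". Its stated purpose is different, however: "To explore the impact of selected baseline factors in addition of study intervention".

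**The concern.** Blocking within prognostic strata balances the arms on those factors, so part of the chance variation in the log-rank numerator is removed by design. The unstratified variance still counts that variation. It is therefore too large, and the test rejects less often than its nominal level under the null. Mixing strata with different underlying hazards also dilutes the treatment effect. Both effects cost power, and both disappear if the factors are not prognostic.

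At stake is some sensitivity on secondary and exploratory endpoints such as time to first seroclearance, time to HBsAg thresholds and time to flare. The plan gives no reason for treating this test differently from its other comparisons.

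**Working it through.** **1. The plan's own power figure.** It belongs to the primary endpoint: 40 vs 80 participants, 5% vs 25%, one-sided 0.05.
- Pooled rate: (0.05 × 40 + 0.25 × 80)/120 = 22/120 = 0.1833.
- Null SE: √(0.1833 × 0.8167 × (1/40 + 1/80)) = 0.0749.
- Alternative SE: √(0.05 × 0.95/40 + 0.25 × 0.75/80) = 0.0594.
- Power: Φ((0.20 − 1.645 × 0.0749)/0.0594) = Φ(1.29) = 90.2%.

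Exact enumeration of the single-stratum Mantel-Haenszel test gives 91.7%, which agrees with the stated >91%. The documents give no power, event count or hazard ratio (HR) for the log-rank test.

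**2. The two statistics.** At each event time, with d events among n at risk (d₁ and n₁ in the active arm), O − E = d₁ − d·n₁/n and V = d(n₁/n)(1 − n₁/n)(n − d)/(n − 1). The unstratified test is Z = Σ(O − E)/√ΣV over all participants. The stratified test forms O − E and V within each stratum and sums over strata before dividing. A stratum holding only one arm has n₁/n equal to 0 or 1, so it contributes nothing.

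**3. Simulation with all 120 participants.** There were 4,000 trials per scenario.
- From the documents: N = 120, 2:1 allocation, permuted blocks in 8 strata, follow-up to Week 96, one-sided 0.05.
- Assumed: block size 6, factor prevalences 0.3/0.5/0.5, exponential times read at visits, no dropout, and the factor HRs below.
- Control incidence by Week 96 was set at 5%, 15% and 30%, with treatment HRs of 5.6, 2.6 and 2.0. The 5.6 is ln(0.75)/ln(0.95), the planned 25% vs 5% applied to Week 96.

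| Factor HRs | Control incidence | Type I error, unstratified / stratified | Power %, unstratified / stratified | Change from stratifying (points) |
|---|---|---|---|---|
| 1, 1, 1 | 5% | 0.031 / 0.033 | 91.2 / 91.1 | −0.1 |
| 1, 1, 1 | 15% | 0.042 / 0.041 | 74.3 / 73.9 | −0.4 |
| 1, 1, 1 | 30% | 0.048 / 0.049 | 71.9 / 70.8 | −1.1 |
| 2, 2, 1.5 | 5% | 0.032 / 0.035 | 90.2 / 90.8 | +0.6 |
| 2, 2, 1.5 | 15% | 0.039 / 0.043 | 70.9 / 72.9 | +2.0 |
| 2, 2, 1.5 | 30% | 0.040 / 0.043 | 66.2 / 68.5 | +2.3 |
| 3, 3, 1.5 | 5% | 0.031 / 0.035 | 88.8 / 90.5 | +1.7 |
| 3, 3, 1.5 | 15% | 0.041 / 0.047 | 66.9 / 71.7 | +4.8 |
| 3, 3, 1.5 | 30% | 0.033 / 0.045 | 58.6 / 67.2 | +8.6 |
| 5, 7, 2 | 5% | 0.025 / 0.036 | 82.2 / 87.2 | +5.0 |
| 5, 7, 2 | 15% | 0.028 / 0.043 | 55.8 / 70.0 | +14.2 |
| 5, 7, 2 | 30% | 0.023 / 0.048 | 42.9 / 64.8 | +21.9 |

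The Monte Carlo standard error of a 70% power is √(0.7 × 0.3/4000) = 0.7 points. Both tests were run on the same simulated trials. A repeat simulation gave gains of about 1 to 3 points for HRs near 2 and 1 to 8 near 3, and a loss of at most about 1.5 points when the factors were not prognostic.

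**4. Simulation in a baseline-restricted subset.** Some exploratory endpoints admit only participants above or below a baseline cut-off (SAP 5.4.1.3.1 to 5.4.1.3.4). With an assumed 30% eligible, 0.3 × 120 = 36 participants fall into 8 cells, or 4.5 per cell on average. At 30% control incidence and treatment HR 3, power unstratified vs stratified was 63 vs 55% (65 vs 55% on repetition) for non-prognostic factors. It was 57 vs 52% for HRs 2, 2, 1.5, and 47 vs 50% for HRs 3, 3, 1.5. With 20% eligible it was 47 vs 35%, 41 vs 34% and 36 vs 32%. At 20 to 30% eligible, about 94 to 100% of trials had at least one stratum that was empty or held only one arm.

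**The case against.** The strongest reply is that little depends on this. These comparisons are secondary or exploratory, with no multiplicity adjustment (SAP 5.3.2 and 5.4.2). The primary test and the emphasised seroclearance comparisons are already stratum-adjusted. The unstratified test also matches the unstratified Kaplan-Meier curves and medians described beside it. All of this stands, and it sets the severity.

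The strength of the factors is also uncertain. Protocol 2.1 cites "7-fold higher annual HBsAg seroclearance rates in Caucasian patients compared to non-Caucasians", but from a retrospective cohort of patients who had stopped NA after HBeAg seroconversion, and split differently from Asian vs non-Asian. The same section reports conflicting findings on predictors, and a TDF vs ETV difference in the timing of relapse while overall relapse was similar. That evidence concerns stopping NA, whereas the seroclearance clock starts at first dose (SAP 5.3.1.3.1). At the only control rate in the documents, 5%, the gain was 0.6 to 1.7 points for factor HRs near 2 to 3. Some of the conservatism there comes from small numbers and affects both tests (0.031 and 0.033 with no factor effect).

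Four stronger readings are tempting, and the documents do not support them:
- A reader might infer a clash between the log-rank test and the stratified Cox model. That model takes one baseline factor at a time with its interaction with arm. It gives no single overall treatment test to disagree with.
- A reader might infer a false-positive risk. The error is in the conservative direction.
- A reader might take the largest losses in the table as typical. They need very strong factor effects, which the documents do not establish for this trial.
- A reader might want every time-to-event test stratified by eight cells. Step 4 shows that this usually loses power in restricted subsets.

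**Conclusion.** The point holds for endpoints analysed in the full population, and it is minor. The log-rank test is the exception among the main between-arm comparisons, and it leaves out factors that the protocol itself treats as prognostic. Taking both simulations together, the loss is about 1 to 3 points of power for factor HRs near 2 and about 1 to 9 points near 3, and it is larger only for very strong effects. If the factors are not prognostic, stratifying costs about 1 point (at most about 1.5). The sizes rest on assumed factor effects, prevalences, event rates and exponential times; only the direction follows from the design. Type I error is not inflated and the primary analysis is untouched. With 120 participants, sparse cells are not a reason to leave the strata out. In small baseline subsets they are.

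**What to change.** In SAP 5.3.2.3:
- **Full-population endpoints** (time to HBsAg seroclearance, time to the HBsAg thresholds, time to flare): make the log-rank test stratified by the three randomisation factors the between-arm test, and keep the unstratified test as supportive.
- **Pooling rule:** state in advance, without reference to outcomes by arm, what happens when a stratum contains participants from only one arm, for example collapsing to HBsAg level alone. A wholly empty stratum needs no rule, because it contributes nothing.
- **Restricted or sparse endpoints:** keep the unstratified test, or stratify by one factor only. This covers the baseline-restricted endpoints in SAP 5.4.1.3.1 to 5.4.1.3.4 and time to virologic breakthrough (SAP 5.3.1.3.3). Few breakthroughs are likely, since Protocol 2.2.1 reports none in the arms combining JNJ-6379 or placebo with NA. Virologic flare under Derivation 2, which is limited to participants with quantifiable HBV DNA at the end of treatment, fits here too.

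The change needs no new data and no design change, and the protocol's wording does not exclude a stratified log-rank test. It has two costs. One is the small loss if the factors turn out not to be prognostic. The other is documentation: the sponsor's central team is to be unblinded at the Week 48 interim analysis (SAP 1.5), and the SAP amendment history already refers to past interim analyses. The amendment should therefore be dated, justified, and shown to precede the analysis it governs.
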